9.4.3.2 Comparator Drug

Not applicable.

9.4.3.3 Labeling for Study Drug

H3B-6527 will be labeled in accordance with text that is in full regulatory compliance with each participating country and is translated into the required language(s) for each of those countries. Study drug labels will not bear any statement that is false or misleading in any

manner or represents that the study drug is safe or effective for the purposes for which it is being investigated.

9.4.3.4 Storage Conditions

Study drug will be stored in accordance with the labeled storage conditions. At the study center, study drug is to be stored refrigerated at 2-8°C.

Subjects will be instructed to store study drug at home according to the storage requirements listed on the drug supply label.

While at the study center and at home, the study participants will be instructed to take capsules immediately after removal from refrigerated conditions, in order to limit the time out of the required storage conditions.

9.4.4 Method of Assigning Subjects to Treatment Groups

The dose level to which a subject is assigned is dependent on the study part and cohort into which the subject is enrolled.

9.4.4.1 Dose Escalation Scheme (Part 1)

The starting dose of H3B-6527 is 300 mg QD.

H3B-6527 doses will be escalated sequentially after the SRC, with appropriate representation from the Sponsor and participating investigators, reviews safety data collected during C1 from the subject(s) enrolled at the current dose level.

Subjects who do not receive study drug for at least 17 of 21 days (approximately 80%; not necessarily consecutively) during the first cycle for reasons not considered to be a DLT by both the investigators and the Sponsor will be replaced. The subjects who are replaced will not be considered evaluable for DLT assessments.

Based on the interim evaluation of the safety and tolerability data of the previous dose level, the Sponsor may decide to initiate accrual at an intermediate dose level. The SRC may be convened earlier at the discretion of the Sponsor if important safety issues arise requiring the attention of the committee.

Up to 3 subjects initially are to be enrolled. After 3 subjects complete C1 and have safety evaluations performed through C2 Day 1, and:

- None of these 3 subjects experience a DLT (see [Section 9.1.1.1.1](#)), then enrollment of the next cohort may commence with approval from the SRC.
- 1 of 3 subjects within a cohort experiences a DLT (see [Section 9.1.1.1.1](#)), then up to 3 additional subjects are to be enrolled sequentially at that dose level. If none of the

additional 3 subjects has a DLT (ie, 1 of 6 subjects has a DLT), then enrollment at the next scheduled dose may commence with approval from the SRC.

- If ≥ 2 subjects within a cohort experience a DLT (see [Section 9.1.1.1.1](#)), then the DLT dose level will have been reached and the previous lower dose level will be considered the MTD. Note that at least 6 subjects must be treated at the dose level potentially considered to be the MTD before that dose level can definitely be considered the MTD. Therefore, if ≥ 2 subjects within a cohort experience a DLT and the previous dose level did not enroll 6 subjects, enrollment will move down to the previous dose level and continue until 6 subjects are enrolled, and the same guidelines for determining the MTD will be followed.
 - Once the MTD or RP2D is established, additional subjects will be treated in the Expansion phase of the study (Part 2), which is designed to better characterize the safety, tolerability and preliminary antitumor activity of the study drug when provided at the RP2D and schedule.

Due to the potential for dropouts during the first cycle of treatment (eg, because of early disease progression), a cohort may initially be expanded to include up to 2 additional subjects. However, if these additional subjects are to be enrolled, they must start treatment ≤ 14 days after the third subject enrolled in the cohort was first dosed with H3B-6527. The decision to dose escalate may still be made after the third subject enrolled to the dose level in question has completed the first cycle of treatment. However, if under these circumstances the decision is made to enroll subjects to a higher dose level, and one of the additional subjects treated at the preceding dose level experiences a DLT in the first cycle of treatment, then further enrollment of subjects to the higher dose level will be suspended until it can be determined whether the preceding dose level exceeds the MTD. In the meantime, subjects enrolled to the higher dose level may continue treatment at that dose if they are tolerating it well, and if continuing treatment is considered appropriate for the toxicity in question. Although decisions regarding dose escalation will be made based on review of data from C1, safety data will also be collected from all subjects continuing treatment and this will be reviewed periodically by the SRC. Any detected cumulative toxicity may require later dose reductions or other action as appropriate, including further refinement of the RP2D.

The dose escalation procedure is summarized in Table 3.

Table 3 Summary of Dose Escalation Procedure

Observed Safety Outcomes	Action
Dose Escalation Cohorts (n=3-6 each)	
No DLT	
 • Escalate to the next planned dose level.
DLT in 1 of 3 subjects	
 • Expand cohort up to 6 subjects.
No additional DLT in 6 subjects	
 • Escalate to the next planned dose level.
DLT in ≥ 2 subjects	
 • MTD reached; stop dose escalation. • Possibly explore intermediate doses for the RP2D.

Note: DLT is defined in [Section 9.1.1.1.1](#).

DLT = dose-limiting toxicity, MTD = maximum tolerated dose, RP2D = recommended Phase 2 dose.

If PK, pharmacodynamic, or safety data for H3B-6527 suggest that it may be preferable to administer H3B-6527 BID rather than QD, then the dose escalation procedure may be repeated for BID dosing. In this event, a new cohort of 3 subjects will be enrolled and treated with a BID dose; the initial total daily dose given BID will be equal to a total daily dose that has been well tolerated as a QD dose (DLT rate <33% in a cohort of 3-6 subjects). If BID administration of H3B-6527 is well tolerated in this initial cohort, then dose escalation may continue with BID dosing, following the same dose escalation rules applied to QD administration.

Furthermore, additional cohorts of subjects may be enrolled to evaluate a less frequent dosing schedule (eg, daily for 2 consecutive weeks every 3 weeks [dosing on Day -14 of a 21-day cycle]).

9.4.4.2 Expansion (Part 2)

In the Dose Expansion Phase, all subjects will receive H3B-6527 at the MTD or RP2D for a specific schedule as identified in the Dose Escalation Phase of the study.

9.4.5 Selection of Doses in the Study

The starting dose of H3B-6527, 300 mg (first-in-human dose), is the HED of 1/6th the HNSTD in dog. Dose escalation will follow a modified Fibonacci design such that the magnitude of the escalation will decrease as the dose level approaches the HED of the HNSTD in dogs (HED \approx 2000 mg).

9.4.6 Selection and Timing of Dose for Each Subject

H3B-6527 will be supplied as 50-, 100-, and 200-mg capsules. The starting dose will be 300 mg/day PO, with escalation of total daily doses in successive cohorts to a maximum planned dose of 2000 mg (see [Section 9.1.1.1](#)).

During Parts 1 and 2, subjects will be instructed to take the dose in conjunction with a meal at approximately the same time each day (see [Section 9.2](#)).

Capsules should be swallowed whole. Dosing should not be repeated if a subject vomits. For subjects on a QD schedule, a dose missed by >8 hours should be skipped. For subjects on a BID schedule a dose missed by >4 hours should be skipped.

9.4.7 Blinding

The study will not be blinded.

9.4.8 Prior and Concomitant Therapy

Any medication (including over-the-counter medications) or therapy administered to the subject during the study (starting at the date of informed consent) will be recorded on the Prior & Concomitant Medication Case Report Form (CRF) or Non-Pharmacological

Procedures CRF. The investigator will record on the Adverse Event CRF any AE for which the concomitant medication/therapy was administered.

9.4.8.1 Prohibited Concomitant Therapy and Procedures

The following therapies and procedures are prohibited during study participation:

- Other investigational drugs.
- Other antitumor therapies such as chemotherapy, surgical resection, or antitumor immunotherapy.
- Proton pump inhibitors.
- Radiotherapy for central metastases (eg, vertebral, mediastinal) will not be allowed; the need for such radiotherapy while on study will be seen as an indication of disease progression and the subject should be withdrawn from therapy. However, palliative radiotherapy for up to 2 local peripheral metastases not being used as target lesions is allowed but the need for such therapy may be an indication of PD and should be discussed with the Sponsor prior to implementation.
- Drugs that are strong inhibitors or inducers of CYP3A4 enzyme (see list in Table 4) or P-glycoprotein transporter.
- Drugs that raise serum calcium and phosphorus levels (eg, vitamin D supplements, calcium dietary supplements, calcium antacids) or systemic corticosteroids. The duration between the last systemic corticosteroid administration and the first dose of study drug should be at least 2 weeks. If a short-term course of systemic corticosteroids is required while on treatment, then study drug must be held while the subject receives systemic corticosteroid treatment. If the subject has not progressed in the interim, resumption of treatment with H3B-6527 may be considered following discontinuation of steroid treatment and a 2-week washout period.

Table 4 Inducers and Strong Inhibitors of CYP3A4

INDUCERS
Carbamazepine, efavirenz, nevirapine, phenobarbital, phenytoin, pioglitazone, rifabutin, rifampin, St. John's Wort, troglitazone
STRONG INHIBITORS
Indinavir, nelfinavir, ritonavir, clarithromycin, itraconazole, ketoconazole, nefazodone

Source: [Indiana University Department of Medicine. <http://medicine.iupui.edu/clinpharm/ddis/clinical-table>](http://medicine.iupui.edu/clinpharm/ddis/clinical-table) Accessed September 7, 2016

9.4.8.2 Permitted Concomitant Therapy and Procedures

Medications and treatments other than those specified in [Section 9.4.8.1](#), including palliative and supportive care for disease-related symptoms, are permitted during the study. Subjects should be closely monitored, and treatment is to be instituted for disease-related symptoms, as appropriate.

- Growth Factors: Subjects receiving recombinant erythropoietin or darbepoietin- α prior to study start may continue to receive pretreatment doses. Following initiation of study treatment, the use of erythropoietic and granulocyte growth factors is permitted in accordance with local practice or guidelines. American Society for Clinical Oncology guidelines may be implemented at the discretion of the treating physician.
- Management of diarrhea: Subjects should be instructed to take loperamide, 4 mg, at the occurrence of the first loose stool and then 2 mg every 2 hours until they are diarrhea-free for at least 12 hours. During the night, subjects may take 4 mg of loperamide every 4 hours. Subjects should be advised to avoid dehydration through adequate fluid intake. Bile acid sequestrants may be utilized in the case of bile acid diarrhea.

Medications for the treatment of AEs or cancer symptoms, eg, packed red blood cells and pain medications, are allowed. Additionally, medications (not addressed above) used to treat underlying medical conditions at study entry including antiemetics and antidiarrheals will be allowed to continue.

Management of hyperphosphatemia or hypercalcemia: Phosphorus and calcium will be measured at screening, before the first dose, every week with safety labs during C1, and on Day 1 and Day 8 for C2 and beyond. Please note that a treatment cycle is 21 days. Subjects with elevated levels of phosphorus or calcium at screening, as defined as being over the ULN on local lab ranges, may not participate in this study and should be referred for management of such. If successfully controlled, subjects may be rescreened. During study participation, any confirmed levels of phosphorus above 7 mg/dL, or calcium equal to or above Grade 2 hypercalcemia as per CTCAE, Version 4.03, will result in the dose of H3B-6527 being held for 14 days. The hyperphosphatemia and / or hypercalcemia should be managed by local practice, with medication, diet change and potential referral as necessary. After 14 days of holding the drug, if the phosphorus level has returned to 5.5 mg/dL or lower, and the calcium is less than or equal to a Grade 1 elevation, the subject may begin taking H3B-6527 again at one dose level lower than their original dose and should continue other measures initiated during the drug holiday, such as phosphorus lowering agents, while on study. If a subject should experience hyperphosphatemia above 7 mg/dL or hypercalcemia equal to or above Grade 2 again on study, then study therapy will be discontinued.

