Once a subject has completed C3 at the initially assigned dose schedule and dose level (QD or BID), intrapatient dose escalation will be allowed. Only subjects who have not progressed on treatment and did not have a dose reduction or interruption because of a drug-related AE, will be permitted to escalate to the highest dose level that has completed DLT assessment within that dose schedule and has been shown to be safe (no DLT in the first 3 subjects or no more than 1 DLT in 6 subjects). Subjects on the intrapatient dose escalation will not be included in the DLT analysis at the higher dose level. The investigator and the medical monitor must agree that dose escalation is appropriate for the subject prior to escalating their H3B-6527 dose level.

The starting dose of 300 mg QD (first-in-human dose) is the HED of 1/6th the HNSTD in dog. Dose escalation will follow a modified Fibonacci design such that the magnitude of the escalation will decrease as the dose level nears the HED of the HNSTD in dogs (HED \approx 2000 mg).

Table 1 Dose Cohorts in H3B-6527 Dose-Escalation

Dose Level	Initial No. of Subjects	H3B-6527 Total Daily Dose
-1	3	150 mg
1 ^a	3	300 mg
2	3	600 mg
3	3	1000 mg
4	3	1400 mg
5	3	2000 mg

These total daily dose levels may be evaluated in QD or BID dose schedules, including intermediate dose levels, and in expansion of an existing dose level of up to 12 evaluable subjects following discussions between the Sponsor and the investigators, if supported by evolving safety, tolerability, PK, and pharmacodynamic data.

BID = twice daily, PK = pharmacokinetic, QD = once daily.

a: Planned starting dose level in QD schedule.

Refer to [Section 9.4.4.1](#) for details regarding the dose-escalation procedure.

The MTD is defined as the highest dose at which no more than 1 of 6 subjects experiences a DLT in the dose cohort. (Note that at least 6 subjects must be treated at the dose level potentially considered to be the MTD before that dose level can be considered the MTD). Therefore, if ≥ 2 subjects within a cohort experience a DLT and the previous dose level did not enroll 6 subjects, enrollment will move down to the previous dose level and continue until 6 subjects are enrolled, and the same guidelines for determining the MTD will be followed.

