Hematology	
• Febrile neutropenia• CTCAE Grade 4 neutropenia that does not resolve to Grade ≤ 2 within 7 days• CTCAE Grade 3 thrombocytopenia requiring transfusion• CTCAE Grade 3 thrombocytopenia and clinically significant bleeding• CTCAE Grade 4 thrombocytopenia• CTCAE Grade 3 anemia if transfused or if lasting for more than 7 days• CTCAE Grade 4 anemia of any duration
Gastrointestinal	
• CTCAE Grade 3 nausea, vomiting and/or diarrhea lasting more than 72 hours despite the use of optimal anti-emetic/antidiarrheal treatment• CTCAE Grade 4 diarrhea and/or vomiting irrespective of prophylaxis or appropriate treatment
Renal	
• CTCAE Grade ≥ 3 serum creatinine
Hepatic	
• CTCAE Grade 3 bilirubin ($>3.0 \times \text{ULN}$) and/or AST/ALT $\geq 10 \times \text{ULN}$• For subjects with a starting AST/ALT within the normal range for the local laboratory, an elevation AST/ALT $\geq 5 \times \text{ULN}$ for the local laboratory

Table 2 Definition of Dose-Limiting Toxicity (Cycle 1 Phase 1 Only) or Dose-Modifying Event (Cycle 2 or Beyond and Any Cycle in Phase 2)

TOXICITY	CRITERIA
	
 For subjects with an abnormal value \geq ULN at baseline based on the local laboratory ranges, an AST/ALT elevation $\geq 10 \times$ ULN for the local laboratory
Other AEs not listed above	
 Nonhematologic toxicities of CTCAE Grade ≥ 3 except for the following: 
 CTCAE Grade 3 fatigue lasting less than 1 week Isolated CTCAE Grade 3 elevations in biochemistry laboratory values without associated clinical symptoms that last for ≤ 7 days. This includes electrolyte abnormalities that respond to medical intervention. H3B-6527-related, CTCAE Grade 2 nonhematologic toxicities that, in the opinion of the treating investigator, require a dose reduction or discontinuation of study drug, or lead to a failure to complete at least 17 days of study drug administration in C1, may be deemed dose-limiting if agreed upon by the participating investigator and the Sponsor.

AE = adverse event, ALT = alanine aminotransferase, AST = aspartate aminotransferase, C = Cycle, CTCAE = Common Terminology Criteria for Adverse Events, ULN = upper limit of normal.

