9.4.2 Guidelines for Continuation of Treatment

Study drug should continue to be administered as planned unless a DLT has occurred. Subjects who experience a DLT during C1 will be discontinued from treatment. In rare cases, an exemption to study discontinuation for a DLT in 1st cycle may be considered after discussion between the treating physician, Sponsor and study medical monitor. If a subject should experience a DLT or DME (ie, an AE meeting the criteria for a DLT but occurring after C1) during the study then study treatment will be interrupted and subjects may, at the discretion of the investigator, and after discussion with the Sponsor, be allowed to continue study drug at a reduced dose, if the following criteria are met:

- ANC $\geq 1.0 \times 10^9/L$ (1,000/mm³)
- Platelet count $\geq 75 \times 10^9/L$ (75,000/mm³)
- All other nonhematologic treatment-related toxicities are Grade 0 or 1 (except alopecia) or return to baseline level
- Clinical benefit is being received, and
- Evidence of an otherwise favorable risk/benefit profile.

The magnitude of the dose reduction cannot be specified *a priori* since the actual doses evaluated and the dose-toxicity relationship will not be known until there is clinical experience with H3B-6527; however, a minimum reduction of 33% must be taken. The dose chosen will require discussion and agreement between the investigator and Sponsor following review of the relevant clinical data.

Dose reductions are allowed for all subjects. However, once the H3B-6527 dose has been reduced for a given subject, no re-escalation will be permitted for that subject.

A maximum of 2 dose reductions will be allowed as needed, but study treatment should not be resumed in the case of the following treatment-related events:

- Occurrence of a DLT in C1 except upon agreement with investigator, Sponsor and medical monitor. A dose reduction must be taken if treatment is resumed.
- CTCAE Grade 3 or 4 cardiac event
- Nonhematologic events of Grade 4 severity
- Dose delay of ≥ 21 days for a treatment-related event in C2 and beyond.

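### At 2000 mg and 1400 mg, restarting one dose level lower after a calcium or phosphorus hold falls short of the 33% minimum reduction when the event is also a dose-modifying event or an exempted Cycle 1 DLT

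*Protocol*

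**What the plan says.** **Mineral hold.** Protocol section 9.4.8.2, and the synopsis under management of hyperphosphatemia or hypercalcemia, set a trigger of phosphorus above 7 mg/dL or calcium of Grade 2 or worse. That "will result in the dose of H3B-6527 being held for 14 days". If phosphorus has then fallen to 5.5 mg/dL or less and calcium is no worse than Grade 1, the subject may restart "at one dose level lower than their original dose".

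**DLT or DME.** Section 9.4.2, and the matching part of the synopsis, begin "If a subject should experience a DLT or DME" and allow treatment to continue at a reduced dose if recovery criteria are met. The size of the cut is left to the investigator and Sponsor, with a floor: "a minimum reduction of 33% must be taken". The same section bars resumption after treatment-related nonhematologic Grade 4 events. It also bars it after a Cycle 1 DLT unless the investigator, Sponsor and medical monitor agree.

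**What counts as a DLT or DME.** Under section 9.1.1.1.1 the event must be judged related to study drug. Table 2 then counts nonhematologic toxicity of Grade 3 or worse, with an exception for "Isolated CTCAE Grade 3 elevations in biochemistry laboratory values without associated clinical symptoms" that last no more than 7 days. It adds that the exception covers electrolyte abnormalities that respond to medical intervention. Separately, a related Grade 2 nonhematologic toxicity that needs a dose reduction may be deemed dose-limiting by agreement. A Table 2 event in Cycle 2 or later, or in any cycle of Phase 2, is a DME.

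**Dose levels.** Table 1 lists total daily doses of 150, 300, 600, 1000, 1400 and 2000 mg, and its note allows other levels ("including intermediate dose levels").

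**The concern.** One calcium event can trigger the mineral hold and also be a DME. Two provisions then set the restart dose: one by counting levels, the other by a percentage floor. Neither section refers to the other, and nothing says which takes precedence. If a one-level step is smaller than the floor, a site cannot follow both as written.

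What is at stake is consistent handling. Two subjects with the same event at the same high dose could be restarted differently depending on which section the site read, and the reasons for their dose reductions would not be comparable. Hyperphosphatemia with focal mineralization is among the potential toxicities listed in section 7.1.1.3, so mineral disturbances are anticipated in this study.

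**Working it through.** The plan gives no derived figure to reproduce: 33% is a fixed rule and the doses are a fixed list. The check compares the two.

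**Step 1. Size of a one-level step.** Reduction = 100 × (D − next lower level) / D, with D from Table 1. The highest dose that satisfies the floor is 0.67 × D.

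| From (mg) | To (mg) | Reduction | Highest dose meeting the 33% floor (mg) | Floor met by one level? |
|---|---|---|---|---|
| 2000 | 1400 | 600/2000 = 30.0% | 1340 | No, short by 3.0 points |
| 1400 | 1000 | 400/1400 = 28.6% | 938 | No, short by 4.4 points |
| 1000 | 600 | 400/1000 = 40.0% | 670 | Yes |
| 600 | 300 | 300/600 = 50.0% | 402 | Yes |
| 300 | 150 | 150/300 = 50.0% | 201 | Yes |

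**Step 2. Can an event fall under both rules?**

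- *Grade 3 hypercalcemia, related.* It triggers the hold (Grade 2 or worse). It meets Table 2 if it is symptomatic, is not isolated, or lasts more than 7 days, subject to how the electrolyte sentence is read. A symptomatic event stays outside the exception on any natural reading.
- *Grade 2 hypercalcemia, related.* It triggers the hold, and section 9.4.8.2 itself attaches a reduction to restart. It becomes dose-limiting only if the investigator and Sponsor agree.
- *Grade 4, related.* Section 9.4.2 bars resumption, so there is no 33% restart dose to compare. Section 9.4.8.2 states no such upper limit, which is a second mismatch between the same sections.
- *Phosphorus above 7 mg/dL.* The documents give no CTCAE grade for this value. It is affected only if the event is judged to meet Table 2.

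**Step 3. Can such a subject reach restart under both sections?** Yes. Section 9.4.8.2 requires calcium no worse than Grade 1. Section 9.4.2 requires nonhematologic treatment-related toxicity at Grade 0 or 1, or back to baseline. These are compatible. The 14-day hold is shorter than the delay of 21 days or more that bars resumption from Cycle 2 on, so that bar does not by itself remove the overlap.

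**Step 4. When?** A Cycle 1 DLT in Part 1 normally ends treatment, with exemption only in rare cases. The overlap therefore arises mainly as a DME: from Cycle 2 in Part 1, or in any cycle of Part 2.

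**Step 5. Effect of intermediate levels.** A new level between 1400 and 2000 mg, or between 1000 and 1400 mg, makes the one-level step smaller and widens the shortfall. A new level above 670 mg and below 1000 mg would create the same conflict at 1000 mg. The shortfall would vanish only if an intermediate dose replaced the next Table 1 row and lay at or below the limit in the table above.

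**The case against.** The strongest reply is that this is a rare overlap with a workable reading. Section 9.4.8.2 is permissive about restarting, whereas section 9.4.2 is mandatory and requires investigator and Sponsor to agree the dose, so a DME subject would be reviewed before any restart. Alternatively, the mineral rule is the specific one and displaces the general one. Intermediate levels are allowed, so one level lower need not mean the next row of Table 1. The electrolyte sentence in Table 2 may also exempt many of the subjects who recover well enough to restart.

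Much of this stands as a limit on frequency. It does not remove the conflict. The permissive wording concerns whether to restart; once a subject restarts, the dose is stated. The two readings above lead to different doses, and the protocol chooses neither. The electrolyte sentence does not clearly cover symptomatic Grade 3 events, and it does not touch the Grade 2 route.

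A reader might infer more than the documents support:

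- *That every mineral hold at the top two doses breaches the floor.* It does not. The 33% rule binds only after a DLT or DME, and the hold itself has no relatedness test.
- *That Grade 4 events, or all phosphorus events, are caught.* The first are barred from resuming if treatment-related. For the second, no grade is given.
- *That a figure was miscalculated, or that the MTD, an endpoint or subject safety is shown to suffer.* No figure is wrong. DLT status is set by Table 2, whatever the restart dose. The exposure summary in SAP section 5.6.1 counts a 30% or a 33% cut alike as a reduction, although dose intensity could differ slightly.

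**Conclusion.** The inconsistency is real, narrow and minor. For a related hypercalcemia event that triggers the hold and is also a DME (or a Cycle 1 DLT exempted from discontinuation), the one-level restart and the 33% floor cannot both be met with the Table 1 levels at 2000 mg (30.0%) or 1400 mg (28.6%). They are compatible at 1000, 600 and 300 mg. It is a contradiction between two stated rules rather than an arithmetic error.

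This rests on three assumptions: that dose level means the rows of Table 1, that the event is judged drug-related, and that it falls outside the Table 2 exception or is deemed dose-limiting by agreement. The documents do not show how many subjects received the two highest doses, so the number affected cannot be estimated. No view is taken on which rule or dose is right.

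**What to change.** Reconcile section 9.4.8.2 and the synopsis text on hyperphosphatemia and hypercalcemia with section 9.4.2 and the synopsis text on continuation of treatment. State which restart provision governs when a phosphorus or calcium event also meets DLT or DME criteria. The same sentence should say whether the bar on resuming after related Grade 4 nonhematologic events applies to mineral holds. The choice is the sponsor's.

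The cost is one clarifying sentence, placed in the body and repeated in the synopsis. It needs no new data and no change to the SAP.
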